6.5. Demographic, Safety, Feasibility and Efficacy Data

Demographic and baseline clinical and disease characteristics will be summarized in tables. For continuous variables, the summary will include number, mean, and standard deviation and 95% confidence intervals. Summaries for categorical variables will include the number and percent of subjects in each category.

6.6. Imputation of Missing Data

Imputations for missing data in (e.g. withdrawn subjects, loss to follow-up, missing data) will not be performed. Analyses will be performed with all available data only.

7. Adverse Event and Incident Reporting

The occurrence of Adverse Events will be monitored during this study. All Adverse Events will be recorded on the Adverse Event Form and followed until resolved. The study will be conducted in accordance with EN ISO 14155: 2018-08: Clinical investigation of medical devices for human subjects - Good Clinical Practice. All Serious Adverse Event will be adjudicated by an independent DSMB and adjudicated results will be included in the data analysis.

 neuroloop	Confidential	Protocol – The baroloop Study
--	---------------------	-------------------------------------

7.1. Adverse Event (AE)

An **Adverse Event (AE)** is any untoward medical occurrence, unintended disease or injury or any untoward clinical signs (including an abnormal laboratory finding) in subjects, users or other persons whether or not related to the medical device. This includes events related to the device or events related to the procedures involved.

An **Adverse Device Effect** is an adverse event related to the use of a medical device, including adverse events resulting from insufficient or inadequate Instructions for Use, deployment, implantation, installation or operation, or any malfunction of the medical device or any event resulting from user error or intentional misuse of the medical device.

The Investigator is responsible for assessing the severity of the AE, the causal relationship between any events and the clinical study procedure, activities or device. Additionally, the Investigator is responsible for providing appropriate treatment for the event and for adequately following the event until resolution. The following categories of adverse event severity are to be used:

- **Mild:** Awareness of a sign or symptom that does not interfere with the subject's usual activity or is transient, resolved without treatment and with no clinical sequelae.
- **Moderate:** Interferes with the subject's usual activity.
- **Serious:** Any fatal or immediately life-threatening clinical experience that requires a subject to be hospitalized, or hospitalization is unduly prolonged because of potential disability or danger to life or because an intervention has been necessitated. This includes any permanently disabling event.

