4.2. Primary Study Endpoints

4.2.1. Safety

Composite Major Adverse Event (MAE) Rate at six (6) months post-treatment including:

- All-causes of death
- Hospitalization for hypertensive crisis post-titration
- Any device or procedure-related serious adverse event

All MAEs will be adjudicated by an independent Data Safety Management Board (DSMB).

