7.2. Serious Adverse Events (SAE)

A **Serious Adverse Event (SAE)** is any problem or unwanted event encountered in a clinical trial or a performance evaluation that has led, or could have led, directly or indirectly to death or to a serious deterioration in the health of a subject or user or any other person, without regard to whether the event was caused by a medical product. The following events (including laboratory results and outcome events) will be considered to be SAEs and must immediately (within 24 hours) be reported to the study Sponsor and / or designated representative by telephone, fax and / or email. These events must be reported whether or not the Investigator believes they are related to study procedures, activities or device:

- Death
- Serious deterioration in the health of the subject, that either resulted in
 - a life-threatening illness or injury, or
 - a permanent impairment of a body structure or a body function, or
 - in-patient or prolonged hospitalization, or
 - medical or surgical intervention to prevent life-threatening illness or injury or permanent impairment to a body structure or a body function.
 - chronic disease
- Fetal distress, fetal death or a congenital physical or mental impairment or birth defect

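### Section 7.1 makes Serious the top severity grade, with a definition that does not match the SAE definition in 7.2, so severity and seriousness are conflated

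*Combined protocol and SAP*

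**What the plan says.** Section 7.1 introduces its scale with the words "The following categories of adverse event severity are to be used" and gives three grades. Mild covers transient events or those that do not disturb normal activity. Moderate is defined only as "Interferes with the subject's usual activity". The top grade is called Serious and has three limbs:

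- "Any fatal or immediately life-threatening clinical experience that requires a subject to be hospitalized";
- the case where "hospitalization is unduly prolonged because of potential disability or danger to life or because an intervention has been necessitated";
- a closing sentence, "This includes any permanently disabling event".

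Section 7.2 defines an SAE as an event that "has led, or could have led, directly or indirectly to death or to a serious deterioration in the health of a subject" (or of a user or another person). It then lists the events that count: death, serious deterioration in the subject's health with one of several results, and fetal or congenital harm. One result under serious deterioration is "in-patient or prolonged hospitalization, or". The others are life-threatening illness or injury, permanent impairment of structure or function, an intervention to prevent such harm, and chronic disease.

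Sections 4.2.1 and 6.2 make "Any device or procedure-related serious adverse event" the third component of the composite MAE rate at six months.

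**The concern.** Severity describes how intense an event is. Seriousness is a regulatory classification by outcome. Section 7.1 gives the top severity grade the name of the classification and defines it by outcomes such as death, hospitalization and disability. Two consequences follow.

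First, the scale has no place for an event that is intense but meets none of those outcomes. The investigator must record it as Moderate, alongside events that merely interfere with activity, or label it Serious when it is not. In a first-in-human study the intensity of stimulation-related effects is part of what is to be described, and this scale cannot show it cleanly.

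Second, the protocol carries two non-matching descriptions under the word serious, and the primary safety endpoint uses that word. A site that works from the 7.1 grade when deciding whether to flag an SAE would be applying the wrong test, and for some events a narrower one.

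**Working it through.** **Step 1: set the two texts side by side.** This is a comparison of wording; the plan states no figure that depends on it.

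| Type of event | 7.1 grade Serious, as written | 7.2 SAE |
|---|---|---|
| Serious deterioration leading to admission, not immediately life-threatening | Not met by the first limb | Met |
| Serious deterioration with permanent, non-disabling impairment (e.g. lasting hoarseness, if so judged) | Not met; the closing sentence requires disability | Met |
| Serious deterioration with an intervention to prevent permanent impairment, no admission | Not met; intervention appears only as a reason for prolonged hospitalization | Met |
| Event that could have led to serious deterioration but did not | Not met | Within the opening definition |
| Intense event with none of these outcomes | Not met, so Moderate | Not met |

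The first four rows can be Moderate or lower in 7.1 while falling within 7.2. The last row shows the missing grade.

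**Step 2: test a more generous reading of 7.1.** The first limb is badly worded: taken literally, even a fatal event must also require hospitalization. If hospitalization alone is allowed to qualify, the first row drops out. The next three rows remain, and so does the missing grade. Section 5.3 lists infection, hematoma, voice alteration and nerve injury as potential events, so the rows are not far-fetched in this population.

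**Step 3: trace the route to the endpoint.**

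- The endpoint term is the one 7.2 defines. Nothing in 4.2.1, 6.2 or Section 7 routes the MAE count through the 7.1 grade.
- Section 7.8 requires SAEs, and also possible device- or procedure-related adverse events, to reach the sponsor within 24 hours. The latter carry no condition on grade.
- The contents that 7.8 lists for the report include severity and relationship, but no seriousness criterion.
- DSMB adjudication is specified for SAEs (introduction to Section 7) and MAEs (4.2.1), not for all adverse events.

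A related event graded Moderate and not flagged as an SAE would thus reach the sponsor but has no stated route to the DSMB.

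**Step 4: size of one misclassified subject.** Input: up to 10 subjects (Section 4.4). With n = 10 and no other MAE in that subject, the change is 1/10 = 10 percentage points. Exact (Clopper-Pearson) 95% limits for x events are the 2.5% point of Beta(x, n − x + 1) and the 97.5% point of Beta(x + 1, n − x):

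- 0/10 = 0%, interval 0 to 30.8% (upper limit 1 − 0.025^(1/10) = 0.308);
- 1/10 = 10%, interval 0.3% to 44.5%.

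Ten is a maximum. If 4 implant failures, the most that Section 6.1 accepts, left 10 − 4 = 6 subjects in a technical-success analysis, the step would be 1/6 = 16.7 points.

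**The case against.** The strongest reply is that there is only one definition of the endpoint term. Section 7.2 bears that title, and Section 7.3 defines a serious adverse device effect by the consequences of an SAE, not by the 7.1 grade. Section 7.1 calls its list severity categories and never says they decide SAE status. Related events go to the sponsor whatever their grade, monitors review all adverse events (9.7), and the Medical Monitor and DSMB review SAEs. There is also no numerical MAE threshold: acceptability is a DSMB judgement (6.1, 9.13). The Adverse Event Form is not among the documents and may already hold a separate seriousness field.

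Most of this stands. A reader might infer that the primary safety count depends on which of two definitions the analyst picks. The documents do not support that, because 7.2 can reasonably be taken as governing.

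A reader might also infer that 7.2 makes every admission an SAE. It does not: the item sits under serious deterioration in health, and the note in 7.3 excludes planned hospitalization without such deterioration.

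The reply does not remove the missing intensity grade. Nor does it change the fact that no sentence says the 7.1 grade plays no part in deciding seriousness.

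**Conclusion.** The point holds as a defect of definition with a limited, residual bearing on the primary safety endpoint. Section 7.1 conflates severity with seriousness, and its Serious text fails to cover some events that 7.2 makes SAEs. The endpoint is at risk only if a site uses the 7.1 grade to decide SAE status and the sponsor, CRO or monitor does not correct it. In that case a qualifying related event could miss DSMB adjudication. Deaths and hospitalizations for hypertensive crisis are separate MAE components and need not depend on this route.

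The size is 10 percentage points per affected subject, assuming 10 subjects in the denominator and no other MAE in that subject. How many such subjects to expect cannot be estimated. A reader might multiply the 8.5% surgical complication rate in Section 2.5.2 by 10, obtain 0.85, and infer about one event of this kind. That rate covers all surgical complications of vagal nerve stimulation. The documents do not say what share would be SAEs, or what share of those would be graded Moderate in 7.1, so the expected number could be close to zero.

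**What to change.** In Section 7.1, replace the grade Serious with Severe and define it by intensity only, for example as preventing usual activity. Remove the references to death, hospitalization and disability from that grade.

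Add one statement to 7.1 or 7.2: seriousness is determined only by 7.2, is recorded separately from severity, and is the only definition used for SAE reporting, DSMB adjudication and the MAE endpoint. Add the applicable 7.2 criterion to the report contents listed in 7.8.

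The cost is one definition, one or two sentences and at most one extra field on the Adverse Event Form, which may already exist. No additional visits or measurements are needed.

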7.2. Serious Adverse Events (SAE)

A **Serious Adverse Event (SAE)** is any problem or unwanted event encountered in a clinical trial or a performance evaluation that has led, or could have led, directly or indirectly to death or to a serious deterioration in the health of a subject or user or any other person, without regard to whether the event was caused by a medical product. The following events (including laboratory results and outcome events) will be considered to be SAEs and must immediately (within 24 hours) be reported to the study Sponsor and / or designated representative by telephone, fax and / or email. These events must be reported whether or not the Investigator believes they are related to study procedures, activities or device:

- Death
- Serious deterioration in the health of the subject, that either resulted in
 - a life-threatening illness or injury, or
 - a permanent impairment of a body structure or a body function, or
 - in-patient or prolonged hospitalization, or
 - medical or surgical intervention to prevent life-threatening illness or injury or permanent impairment to a body structure or a body function.
 - chronic disease
- Fetal distress, fetal death or a congenital physical or mental impairment or birth defect

7.3. Serious Adverse Device Effect (SADE)

A Serious Adverse Device Effect is an adverse device effect that has resulted in any of the consequences of a Serious Adverse Event.

NOTE: Planned hospitalization for a pre-existing condition, a condition unrelated to the treatment or a procedure required by this study, that is without serious deterioration in health, is not considered a serious adverse event.

7.4. Unanticipated Serious Adverse Device Effect (USADE)

Unanticipated Serious Adverse Device Effect (USADE): Serious adverse device effect which, by its nature, incidence, severity or outcome has not been identified in the risk analysis.

7.5. Anticipated Serious Adverse Device Effect (ASADE)

Anticipated Serious Adverse Device Effect (ASADE): An effect, which by its nature, incidence, severity or outcome has been identified in the risk analysis report.

7.6. Unanticipated Adverse Device Effect (UADE)

Unanticipated Adverse Device Effect (UADE): An adverse device effect which by its nature, incidence, severity or outcome has not been identified in the risk analysis report.

7.7. Anticipated Adverse Device Effect (AADE)

Anticipated Adverse Device Effect (AADE): An effect, which by its nature, incidence, severity or outcome has been identified in the risk analysis report.

7.8. Reporting of Adverse Events (AEs) and Serious Adverse Events (SAEs)

Documentation of all AEs / SAEs: All incidents will be captured as a part of this clinical study. At each contact with the subject, the Investigator will seek information on adverse events by specific questioning and, as appropriate, by examination. Information on all adverse events will be recorded immediately on the Adverse Event Form in the data collection system. All clearly related signs, symptoms, and abnormal diagnostic procedures results should be recorded. .

Reporting of SAEs: All SAEs, UADEs and possible device and / or procedure- related adverse events must be recorded in the Adverse Event Form in the data collection system by the Investigator (or his / her designee) and reported to the Sponsor and its designated representative (MAXIS Medical GmbH) within 24 hours via fax or email. The report should include: Description of incident, severity, duration, action taken, treatment outcome and relationship of the adverse event to the study device, procedure, concomitant medications, pre-existing condition, etc. (i.e., unrelated, relation or relationship unknown).

In the case of serious adverse events (SAE), procedure and / or device failures and malfunctions, medical record documentation (e.g., procedure notes, operative notes, discharge summary, relevant progress notes, imaging or lab studies) must be provided to the Sponsor and its designated representative, if requested .This information shall be faxed or sent by email as requested as soon as possible but latest within 24 hours to the MAXIS Medical / Sponsor. If appropriate, Sponsor shall inform the Competent Authority and the relevant Ethics Committee about the event within the appropriate timelines and in accordance with all national regulations. Reporting of Device Failures and Malfunctions

 neuroloop	Confidential	Protocol – The baroloop Study
--	---------------------	-------------------------------------

All reported device malfunctions or failures of the baroloop System are required to be documented and must be immediately reported to the study Sponsor or its designated representative (MAXIS Medical GmbH) by telephone, fax and / or email within 24 hours. Device failures and malfunctions should also be documented in the subject's medical record. Instructions for returning the investigational device will be provided.

NOTE: Device failures or malfunctions are NOT to be reported as adverse events. However, if there is an adverse event that results from a device failure or malfunction, that specific event would be recorded in the usual way as per the previous chapter.

7.9. Documentation, Evaluation and Notification of Serious Adverse Events

The Investigator shall report all serious adverse events (anticipated or unanticipated) to Sponsor and Sponsor's designated representative within 24 hours upon becoming aware of events.

Authorized Representative / CRO Contact Information:

MAXIS Medical GmbH
[name]
[name]
Germany
[contact]
[contact]
Email: [contact]

Sponsor:

neuroloop GmbH
[name]
[name]
Tel: [name]
Email: [contact]

The Sponsor and / or its designated representative will ensure compliance with all country-specific reporting requirements to the appropriate Ethics Committees and Competent Authorities.

8. Monitoring

The Sponsor or its designated representative, qualified by training and experience, will be responsible for monitoring and overseeing the conduct of the trial. The accuracy of all collected data will be verified for:

- Eligibility criteria
- Baseline characteristics
- Primary safety and feasibility endpoints
- Adverse events
- Secondary endpoints.

Source documents including, but not limited to, medical records, office / clinic notes, procedure reports, laboratory results, physician and nursing progress notes will be verified. Verification

and quality of data, monitoring of clinical study progress and Investigator compliance with the approved protocol will be conducted by the Sponsor or its designated representative (MAXIS Medical GmbH).

The Sponsor or its designated representative (MAXIS Medical GmbH) must be allowed to visit the clinical site and have direct access to all study records throughout the duration of the study. The monitor will review all source data and compare them to the data documented in the case report forms, in addition to performing a review of the Regulatory Binder and conducting device accountability. The Investigator and / or institution will provide direct access to source data / documents for trial-related monitoring, audits, and regulatory review and inspection.

It is important that the Investigator and relevant study personnel are available during the monitoring visits and that sufficient time is devoted to the process.

Additionally, telephone, email contact, and onsite visits will be conducted on a regular basis with the Investigator and the site staff to ensure that the protocol is being followed and to address any issues that may occur during the trial.

If a deficiency is noted during the course of the trial the clinical monitor is required to discuss the situation with the site and the Sponsor (if required) to secure compliance.

9. Study Management

The Sponsor has overall responsibility for the conduct of the study according to EN ISO 14155 as well as any conditions imposed by local and national regulatory authorities.

For this study, Sponsor will have direct responsibilities and will delegate other responsibilities to appropriate and qualified consultants, contractors and / or Contract Research Organizations (CROs). Together, the Sponsor, consultants and CROs will ensure that the study is conducted according to the Clinical Investigational Plan and all applicable and governing regulations. All personnel to participate in the conduct of this clinical trial will be qualified by education and / or experience to perform their tasks.

9.1.3. Clinical Sites

A complete listing of all clinical sites will be maintained by the Sponsor and will be available upon request.

9.2. Ethical Considerations

The rights, safety and well-being of clinical investigation subjects shall be protected consistent with the ethical principles as defined in the Declaration of Helsinki 2013. These principles shall prevail over interests of science and society and shall be understood, observed and applied at every step in this clinical investigation.

It is expected that all parties will share in the responsibility for ethical conduct in accordance with their respective roles in the investigation. The Sponsor and the Investigator(s) shall avoid improper influence or inducement of the subject, monitor, the clinical investigator(s) or other parties participating in or contributing to the clinical investigation.

9.3. Insurance

The Sponsor will maintain the appropriate and necessary insurance coverage for the duration of the study.

9.4. Study Conduct

This study will be performed in accordance with EN ISO 14155:2018-08 Clinical investigation of medical devices for human subjects, -, the Declaration of Helsinki 2013, Council Directive 93/42/EEC, and any applicable regional and / or national regulations. The clinical investigation shall not begin until the required approval has been obtained from the relevant national regulatory authority and the local Ethics Committee. Any additional requirements imposed by the regulatory authority or EC shall be followed.

9.5. Audits and Inspections

The Principal Investigator will also allow and support representatives of the governing EC, the Competent Authority, and other applicable regulatory agencies to inspect all study records, the content of the data collection system, and corresponding portions of the subject's office and / or hospital medical records at regular intervals throughout the trial. The Principal Investigator will provide direct access to source data / documents. These inspections are for the purpose of verifying adherence to the protocol, completeness and exactness of the data and compliance with European Union or other regulatory agency regulations.

The Principal Investigator will inform the Sponsor or the Sponsor's designee should they be inspected by any regulatory agencies. The Sponsor or the Sponsor's designee will also inform the site if they are made aware of a pending inspection by a regulatory agency.

Audits may also be conducted by the Sponsor or the Sponsor's designee to evaluate compliance with the protocol, written procedures, EN ISO 14155:2018-08, and other applicable regulatory requirements. These audits are independent of and separate from routine monitoring visits. The audit results will be documented and communicated to relevant parties, if applicable.

